6.4.3 Exploratory endpoint

The prevalence of retinopathy in patients with T2DM and the level of retinopathy in patients with T2DM in the Department of Cardiology.

6.5 Bias and confounding factors management

6.5.1 Bias

The research hospital of this study selects representative medical centers of different grades distributed in six geographical regions of China. The research population chooses a continuous population of diabetic patients in the Department of Cardiology, including outpatients and inpatients, to reflect the real situation of cardiovascular patients with type 2

diabetes, which reduces the selection bias to a certain extent. The data collection of this study adopts the combination of participants' self-report and retrospective of the case system to ensure the accuracy of the collected survey data and reduce the information bias to a certain extent.

6.5.2 Confounding

The data analysis of this study will stratify the center, gender, age, concomitant medication and other factors, and control and correct the influence of potential confounding factors on the results through multivariate regression analysis. Model assumptions will be checked and, if necessary, appropriate transformations or nonparametric analysis methods will be used.

6.6 Sample size estimation

According to studies published in 2007²⁸ and 2005²⁹, among hypertensive patients with T2DM, the detection rate of albuminuria in 2,473 patients in mainland China was 59.9%, and the detection rate of albuminuria in 5,549 patients in 6 countries in Asia was 58.6%.

There were no pre-defined statistical hypothesis tests and power analyzes for this study. Based on the enrollment of 30 participating units in two different levels (18 in the tertiary level and 12 in the secondary level), assuming a prevalence rate of 50% and a target sample size of 3,000 patients. Therefore, at least 100 cases were selected for each participating unit, which can provide an accuracy of 3.6%, and the 95% CI is 48.2%, 51.8%.

Total number of analysis	Prevalence	Number of related	95% confidence interval	95% confidence interval width (%)
--------------------------	------------	-------------------	-------------------------	-----------------------------------

sets		events		
1,000	50 %	500	46.9% , 53.2%	6.3%
1,500	50 %	750	47.4% , 52.6%	5.2 %
2,000	50 %	1,000	47.8% , 52.2%	4.4%
3,000	50 %	1,500	48.2% , 51.8%	3.6 %
5,000	50 %	2,500	48.6 % , 51.4%	2.8%
9,000	50 %	4,500	49.0 % , 51.0 %	2.0 %

7 Research and Data Management

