2.1 Primary objective

To assess the prevalence of albuminuria in patients who are combined with T2DM and different cardiovascular diseases in inpatient and outpatient cardiology departments of secondary and tertiary hospitals in China.

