3.2 Center distribution

In the 6 major administrative regions of China (North China, East China, Northeast China, Central South China, Southwest China, Northwest China), 30 regionally representative medical centers with more than 50 daily outpatients in the Department of Cardiology were selected, among which 3 tertiary hospitals and 2 secondary hospitals in each district. According to the comprehensive situation of the hospital, a representative cardiology ward will be selected in the inpatient department of each branch center, and several representative outpatient doctors will be selected in the outpatient department.

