3.3 Number of subjects

In this study, 50 patients with T2DM who meet the inclusion and exclusion criteria in the outpatient department of cardiology and 50 inpatients will be continuously included in each sub-center. A total of 100 patients will be included in each sub-center, totaling 3,000

patients. For details on sample size, see 6.6 Sample Size Estimation.

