3.7 Study Population

This study will adopt a stratified, multi-level, and multi-center strategy for continuous screening to enroll patients who meet all inclusion criteria and none of the exclusion criteria.

During the enrollment period, the Clinical Coordinator will communicate with and invite all potential patients attending the selected inpatient wards or the designated outpatient physicians. Screening information, including patient name, gender, age, screening time, successful enrollment, and reasons for enrollment failure, will be recorded using the patient screening form (see Appendix 1). The patient screening form is kept by each sub-center, which is the source document of this study and must not be transmitted to anywhere outside the sub-center. Before conducting any study procedures or questionnaires, the research team will obtain electronic or written informed consent from patients.

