4.3 Research procedure

The patient recruitment consisted of two parts, 50 patients from outpatients attending the Department of Cardiology and 50 from in patients receiving treatment in the Department of Cardiology.

- In the outpatient department, a selected, representative cardiologist should be followed and eligible patients among the physician's visits would be continuously screened. It is necessary to communicate with the person in charge of the Department of Cardiology

[figure not shown]
before the start of the branch center to determine the following outpatient doctors, and plan and determine the enrollment process with the outpatient doctors in advance. On the screening day, record and follow the T2DM patients encountered by the doctor during the consultation process, communicate with the patient for informed consent, screen according to the inclusion criteria, and generate a study number for those who meet the enrollment criteria (see flow chart 1).

- In the ward selected by the inpatient department of the Department of Cardiology, the clinical coordinator conducts a preliminary examination of all inpatients in the ward through the hospital medical record system, records the patient with T2DM, and communicates with the patient for informed consent, according to the inclusion and exclusion criteria, screening is carried out, and those who meet the inclusion conditions are enrolled and a research number is generated (see flow chart 2).

[figure not shown]
A face-to-face questionnaire should be conducted on the enrolled patients and baseline information such as, medical history, clinical assessment information, medication information, and living habits should be collected; and physical examination, UACR tests and funduscopy were performed on the patients. For outpatients, it is also necessary to query all the medical records of the enrolled patients on the day after the day of enrollment to supplement any missing information.

To evaluate the doctor's attention to chronic kidney disease, this study mainly reviewed the doctor's order to observe whether the doctor prescribes the UACR checklist for patients with T2DM to monitor the renal function of the patients. If the doctor has issued a UACR test for the patient, record the inspection value; if the doctor has not prescribed the test, use the

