6.3 Outcome Analysis

6.3.1 Main endpoint

The primary endpoint of this study will be the prevalence of albuminuria (UACR \geq 30 mg/g) in patients with type 2 diabetes presented to the Department of Cardiology , and the prevalence of albuminuria and other demographic characteristics will be assessed by descriptive abstracts. In summary, the relationship between the stage of renal impairment/disease (A1-A3 or GFR classification) and relevant covariates was analyzed by logistic regression model. Crude ORs and multivariate-adjusted ORs will be reported, including covariates including:

Age group (18-39 years old, 40-59 years old, 60-69 years old, \geq 70 years old); gender; BMI group (18.5, 23.9, 27.9, 28), blood pressure, blood lipid (LDL, HDL, TG), living habits (smoking, drinking); sub-research centers, nephrotoxic drugs being used, disease history.

Prevalence will be analyzed grouped by stratification factors, gender and age, geographic

region (East, South, Central, North, Northwest and Southwest), etc.

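### The sample-size section credits 30 centres of 100 patients with a 95% CI width of 3.6 points, which is simple-random-sample precision and ignores clustering by centre

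*Protocol*

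**What the plan says.** Section 6.6 states that there is no planned hypothesis test or power analysis. It assumes a prevalence of 50% and 3,000 patients from 18 tertiary and 12 secondary hospitals, and concludes: "at least 100 cases were selected for each participating unit, which can provide an accuracy of 3.6%, and the 95% CI is 48.2%, 51.8"%. The table below that sentence gives interval limits and widths for totals from 1,000 to 9,000. Each row depends only on the total and the 50% prevalence.

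The design is described elsewhere in the protocol:

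- Section 3.7: "This study will adopt a stratified, multi-level, and multi-center strategy for continuous screening".
- Section 3.2 takes 3 tertiary and 2 secondary hospitals in each of 6 regions. Within each hospital, "a representative cardiology ward will be selected in the inpatient department of each branch center", together with selected outpatient doctors.
- Section 3.3: "A total of 100 patients will be included in each sub-center".
- Section 4.3: "The patient recruitment consisted of two parts, 50 patients from outpatients attending the Department of Cardiology and 50 from in patients".

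The target in section 2.1 is prevalence in "inpatient and outpatient cardiology departments of secondary and tertiary hospitals in China". Centre enters the analysis in two places. Section 6.3.1 includes it in the covariate list ("sub-research centers, nephrotoxic drugs being used, disease history"), and section 6.5.2 says: "The data analysis of this study will stratify the center, gender, age, concomitant medication and other factors". Neither is linked to the precision in 6.6. The protocol mentions no ICC or design effect.

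**The concern.** The sentence in 6.6 is a claim about what 30 units of 100 cases will deliver, but the number attached to it would be the same if 3,000 patients had been drawn independently from the whole country. Patients of one hospital, ward or doctor tend to resemble each other in case mix, referral and treatment. When the target is hospitals in China, the variation between hospitals belongs in the standard error. Leaving it out makes the planned interval too narrow.

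This precision is the only statistical justification for 3,000 patients. If it is overstated, a reader cannot tell what the study can resolve, and a final interval that allows for centre would look like a shortfall against plan.

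A smaller matter sits in the same sentence. It calls 3.6% the accuracy, while the table column shows that 3.6% is the full width. Read as a margin of error, it would be taken as ±3.6 rather than ±1.8 points.

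**Working it through.** **Inputs from the protocol.** Prevalence p = 0.50, N = 3,000, 30 centres, 100 patients per centre (50 outpatients and 50 inpatients), two-sided 95% interval (sections 3.3 and 6.6). Strata: 6 regions × 2 hospital levels = 12 (section 3.2).

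**Input that must be assumed.** The ICC, taken here as the correlation within a centre that remains after stratifying by region and hospital level. The protocol gives none, so a range of 0.005 to 0.05 is shown.

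**Step 1: reproduce the stated figure.** For independent patients:

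- Wald: 0.50 ± 1.96 × √(0.25/3,000) = 48.21% to 51.79%, width 3.58 points.
- Exact binomial, 1,500/3,000: limits 48.195% and 51.805%, width 3.61 points.

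Both agree with the protocol's 48.2%, 51.8% and 3.6%. The arithmetic is correct for a simple random sample, and the number of centres plays no part in it.

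**Step 2: allow for clustering.** Design effect DE = 1 + (m − 1) × ICC, effective N = 3,000/DE, width = 3.578 × √DE. Two cluster sizes bracket the design. With m = 100, all patients of a centre form one cluster. With m = 50, a centre's inpatients and outpatients are treated as uncorrelated, which is the lenient case.

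| Assumed ICC | DE (m = 100) | Effective N | 95% CI | Width, m = 100 | DE (m = 50) | Width, m = 50 |
|---|---|---|---|---|---|---|
| 0 | 1 | 3,000 | 48.2–51.8% | 3.6 | 1 | 3.6 |
| 0.005 | 1.495 | 2,007 | 47.8–52.2% | 4.4 | 1.245 | 4.0 |
| 0.01 | 1.99 | 1,508 | 47.5–52.5% | 5.0 | 1.49 | 4.4 |
| 0.02 | 2.98 | 1,007 | 46.9–53.1% | 6.2 | 1.98 | 5.0 |
| 0.05 | 5.95 | 504 | 45.6–54.4% | 8.7 | 3.45 | 6.6 |

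Example for ICC 0.02, m = 100: DE = 1 + 99 × 0.02 = 2.98, and width = 3.578 × √2.98 = 6.18 points.

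**Step 3: small number of clusters.** With 30 centres in 12 strata there are 30 − 12 = 18 degrees of freedom. The t quantile is 2.101, a factor of 2.101/1.96 = 1.072. The m = 100 widths for ICC 0.01, 0.02 and 0.05 become 5.4, 6.6 and 9.4 points.

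**Step 4: what these ICCs mean.** At 50% prevalence the SD of true centre prevalences is √(ICC × 0.25): 5.0, 7.1 and 11.2 points for ICC 0.01, 0.02 and 0.05. In the protocol's own table, with m = 100, an ICC of 0.01 moves the study from the 3,000 row to about the 1,500 row, and 0.02 moves it to about the 1,000 row.

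**Step 5: how small the ICC must be for 3.6 to survive.** The width still rounds to 3.6 while it stays below 3.65. Starting from the Wald width, the limit is ((3.65/3.578)² − 1)/(m − 1), about 0.0004 for m = 100 and 0.0008 for m = 50. Starting from the exact width of 3.61, it is about 0.0002 and 0.0005.

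**The case against.** The strongest points on the other side are these.

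- **The arithmetic is right.** This stands. The fault is an unstated independence assumption applied to a clustered design.
- **The size is assumed.** This also stands. The protocol gives no between-centre data, so only the direction is certain and the widths are a sensitivity range. The mild case of ICC 0.005 still gives 4.0 to 4.4 points.
- **Clustering matters only if the centres stand for other hospitals.** If the target were these 30 centres alone, clustering by centre would not widen the interval. Section 2.1, however, names secondary and tertiary hospitals in China, and section 6.5.1 relies on the centres being representative. No random draw of centres is described, so a design effect would not cover the uncertainty from purposive selection either. That makes the stated 3.6 no safer.
- **The analysis method may be in the SAP, which is not at hand.** It may well be, and nothing is claimed here about how the final interval will be computed. A cluster-adjusted interval there would not correct the number printed in 6.6.
- **The accuracy wording is minor.** Agreed. The limits and the column heading let a careful reader recover the meaning.
- **The consequence is limited.** The study is descriptive, no test depends on the figure, and the protocol sets no precision threshold that would be breached. This is a reason to keep 3,000 patients, but not to leave the statement as it is.

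**Conclusion.** The concern holds. The precision in 6.6 is that of a simple random sample and is credited to a design of 30 clusters. For the national target, and under an assumed residual ICC of 0.01 to 0.05, the width is about 5.0 to 8.7 points with whole centres as clusters, or 4.4 to 6.6 points in the lenient case, against the 3.6 stated. The direction is firm for any positive ICC. The size depends on an ICC that the protocol does not supply, on equal cluster sizes, and on treating the 30 centres as a sample of hospitals. The calculation covers clustering only, not any weighting. The finding concerns the planning statement and should be fixed, since that statement is the sole statistical basis given for the sample size.

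**What to change.** Keep 3,000 patients and revise section 6.6 as follows.

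1. Label the existing table as precision under simple random sampling.
2. Say that 3.6% is the full width of the interval, that is ±1.8 points.
3. Add an assumed ICC with its basis, the design effect, and the resulting interval for 30 × 100. For example, with whole centres as clusters the expected width is about 5 to 9 points for ICC 0.01 to 0.05.
4. Unless the SAP already does so, state that the interval for the primary prevalence will treat centre as the cluster and region by hospital level as strata. The survey procedures in SAS 9.4, the software already named, can do this. Planned and reported precision then treat centre alike.

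The cost is a few sentences, with no extra patients and no change in conduct. The drawback is that the stated precision becomes less favourable and rests on an ICC that the sponsor must choose and defend.

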7.1 Data collection and management

7.1.1 Confidentiality

The research documents will be properly kept, and the paper originals will be kept by the local research center according to regulations. Electronic files and data will be stored in a non-URL-accessible area, and it is only accessible through the website, and only authorized researchers who have completed training in data handling will have access to the data. Access to the database is controlled by setting the user ID and password system.

All passwords stored in the system will be encrypted using SSL .

7.1.2 Anonymization, de-identification and destruction

Each enrolled patient will be assigned a unique identification code. Any medical records or data sets transmitted to the sponsor will only represent the patient with this code, with any personally identifiable information anonymized. All laboratory reports uploaded to the database according to the regulations must be deprived of privacy before uploading, and

identifiable personal information can be covered before uploading to ensure patient privacy. Biological samples generated during the research will be destroyed immediately after analysis.

7.1.3 Source data

The source data will include original medical records, patient screening forms, instrument inspection reports, questionnaires and case report forms for filling in the data collection site, and all other documents used to record patients' diagnoses and treatment in the hospital. The research center should provide past medical records, including patient medical history, surgical history, and access to various examinations and diagnoses.

7.2 data management

Recording and reporting study data is via paper or electronic case report form (CRF). The researcher needs to sign the paper CRF. Researchers must be responsible for preserving and providing accurate source data. Researchers must allow research-related monitoring, auditing, ethical review, and regulatory agency inspections, and provide source data or documents for their inquiries. The sponsor or designee is responsible for data management of this study, including data quality checks. Unless local regulations or institutional policy require a longer retention period, investigators must ensure that records and documents related to this study (including signed informed consent forms) are retained for 10 years after completion of the study. No records shall be destroyed during the retention period without the written approval of the sponsor. No records shall be transferred to another location or to a third party without written notice to the sponsor.

7.3 Quality control

The researcher must electronically signed CRF before submission. Any obvious errors or omissions in the data or forms that need to be clarified require further inquiries and verification directly with the medical center from which the data originated. Additionally, key data may be double-keyed for additional quality control. During the study period (screening, initiation, enrollment, and end), the sponsor will send monitors to conduct at least one monitoring at each participating research center. The sponsor will organize audits as needed.

8 Regulatory, Ethics and Research Oversight

8.1 Safety and Adverse Events

Although the likelihood of safety issues or adverse events arising from the implementation of this study is small, unexpected conditions (including serious adverse events and adverse events) that may be directly related to the study will be continuously monitored and reported as required. AEs that meet timely reporting requirements will be summarized in a narrative or other form and submitted to the IRB at follow-up review (if there is a follow-up review), or will be recorded and followed up on the patient case report form but not submitted to the IRB (if no follow-up review is required).

8.2 Ethical review and protocol changes

IRB/IEC review and approval were required before initiation. During the research period, if there is any modification to the research documents such as the research protocol and informed consent form, it needs to be reviewed, approved or filed again by the IRB/IEC (according to the specific requirements of the IRB /IEC). During the research period, a

written summary of the research progress shall be provided to the IRB/IEC as required, and the IRB/IEC and other applicable regulations shall be complied with.

The researcher/institution agrees to allow the auditor or monitor to have direct access to all relevant documents, and to arrange time to cooperate with the auditor/monitor to discuss issues and any issues found. Audits and monitoring can be done at any time during or after the study.

8.3 Informed consent procedure

Since no intervention is involved, potential participants will be informed quickly through electronic or paper informed consent, and researchers at each center must explain the following in detail to patients:

- Voluntary participation and the right to withdraw from the study at any time at any stage, without discrimination or retaliation, without affecting the patient's medical care and rights.
- Participation in research and personal data are confidential.
- According to the Declaration of Helsinki, patients should be informed of the nature, purpose, possible expected benefits and risks of the research. Ensure that patients have enough time to consider whether they are willing to participate, and sign the informed consent.
- One original copy of the signed informed consent form was handed over to the patient, and the other original copy was properly kept in the local center.

8.4 Data protection

Investigators must inform participants about how their personal study-related data or medical records will be used, and they must explain to them the extent of disclosure and

that their medical records may be reviewed by authorized personnel designated by the sponsor or by IRB/IEC and regulatory authorities.

8.5 Study Discontinuation

Participants may request to withdraw informed consent and withdraw from the study at any time. The study did not involve an intervention, and adverse events will not be discontinued or the center closed, but adverse events will be recorded in the study file. The sponsor, investigator, or regulatory agency may decide to suspend the study, or part of it, for safety or administrative reasons after reaching an agreement.

Appendix 1

Patient Screening Form

Screening Date	Serial Number	Medical Record Number	Name	Age	Gender	Enrollment Success	Reasons for Enrollment Failure	ID
					 Male  Female	 Yes  No	 Patient Refused Enrollment  Patient Does Not Meet Inclusion Criteria	

Appendix 2

Comparison chart of UACR tester and 14 test papers

Appendix 3

Portable fundus camera

References

1. Aleix Cases Amenós, JRG-J., Pedro Conthe Guti é rrez , Prevalence of chronic kidney disease in patients with or at a high risk of cardiovascular disease. *Rev Esp Cardiol* 2010, 63 (2), 225-228.
2. Galindo, RJ, et al., Clinical characteristics and outcomes of patients with end-stage renal disease hospitalized with diabetes ketoacidosis. *BMJ Open Diabetes Res Care* 2020, 8 (1).
3. Ortiz, A .; Informacion Enfermedades Renales Geneticas , EKPF d. A. pl LC I. E. d. RFRIA d. TR d. IR, RICORS2040: the need for collaborative research in chronic kidney disease. *Clin Kidney J* 2022, 15 (3), 372-387.
4. Gansevoort, RT, et al., Chronic kidney disease and cardiovascular risk: epidemiology, mechanisms, and prevention. *Lancet* 2013, 382 (9889), 339-52.
5. Wen, CP, et al., Diabetes with early kidney involvement may shorten life expectancy by 16 years. *Kidney Int* 2017, 92 (2), 388-396.
6. McMurray, JJV, Urinalysis: A Window to the Heart. *JACC Heart Fail* 2019, 7 (5), 402-403.
7. de Boer, RA, et al., Association of Cardiovascular Biomarkers With Incident Heart Failure With Preserved and Reduced Ejection Fraction. *JAMA Cardiol* 2018, 3 (3), 215-224.
8. Gladden, JD, et al., Heart Failure with Preserved Ejection Fraction. *Annual Review of Medicine* 2018, 69 (1), 65-79.
9. Vaduganathan, M., et al., Prevention of heart failure events with intensive versus standard blood pressure lowering across the spectrum of kidney function and

albuminuria: a SPRINT substudy . *European Journal of Heart Failure* 2020, 23 (3), 384- 392.

